#### 3.5.1 Details of Registration Process

Potential trial patients will be identified on the haematology ward or through the attending haematology team. The Research Nurse (RN) and care teams will screen admission lists daily. All eligible patients will be approached as soon as possible after presentation with AML to obtain informed consent. The local RN/PI/delegate will approach the patient to provide a participant information sheet, answer questions, confirm eligibility and seek their willingness to consent to data collection

Those patients providing consent to participating in the trial, data collection and follow up are enrolled into the trial. The recruited participants will then be given a unique study ID number at randomisation that will be used throughout the study. Patients will be randomised using sealedenvelope.com as described in section 4.

Patients who present out of normal working hours will be identified the next working day.

Patients not eligible to be enrolled in the trial will be entered on the screening log so there is evidence that the patient has been assessed and the reasons for not enrolling are documented.

#### 3.5.2 Informing Trial Participants of Possible Benefits and Known Risks

An information sheet must be provided to the patient at the time of seeking consent, and accompanied by an informed discussion.

#### 3.5.3 Consent

Written informed consent will be obtained from participants before any trial-specific procedures are performed, including taking any blood samples. Participants will be informed that they will be blinded to their allocation and as such will not routinely be informed of their haemoglobin levels during treatment.

The participant is free to refuse to participate in all or any aspect of the trial at any time and for any reason, without incurring penalty or affecting their treatment.

Signed consent forms will be kept by the investigator and the consent discussion will be documented in the medical notes. A copy of the consent form will be provided to the participant, and a copy will be filed in the medical notes of the participant. With consent, a letter will be sent to the participant's general practitioner (GP) informing them of the trial and the participants' involvement in it.

#### 3.5.4 Patients requiring transfusion prior to enrolment

Patients in cycle 1 (without clinically significant bleeding) may be deemed by the clinical team to require transfusion and this be indicated before being approached about the trial to seek consent. These patients may be transfused according to a locally agreed guidelines, which will typically define a threshold of 80 g/L. Once randomisation has occurred (which is anticipated to be on the same working day as consent is obtained) clinicians should adhere to the allocated threshold. All potentially eligible patients must have been randomised before or up to Day 5 from start of chemotherapy.

#### 4. Randomisation

#### 4.1 Randomisation practicalities and blinding

Patients at each site will be randomised using an online randomisation system at sealedenvelope.com. The randomisation number will be recorded on the CRF. Patients will be randomised in a ratio of 1:1 to either the control arm (threshold of  $\leq$ 90 g/L) or the intervention arm (threshold of  $\leq$ 70 g/L) for their first cycle of treatment. The patient will cross-over to the other arm for their second cycle of treatment.

The person on the trial team responsible for undertaking the randomisation procedure will not be the same person who gained consent from the patient.

The participant blinding to the trial allocation arm will be tested with a simple directed question asking which treatment arm the participant considers they are allocated to at each study visit.

#### 4.1.1 Randomisation Practicalities

CRFs must be completed at randomisation/enrolment. Patient details, including diagnosis, centre, haemoglobin concentration and details of transfusions already given must be available before attempting to randomise a patient. Written informed consent must have been obtained before the participant may be randomised.

#### RANDOMISATIONS

To randomise, please visit

# www.sealedenvelope.com

choose the REAL trial from the drop down list and log-on as instructed

If difficulties are experienced using the randomisation website, then please contact the Trial Manager, who will be able to randomise the participant on your behalf.

#### 4.2 Randomisation Codes and Unblinding

Randomisation codes and unblinding are considered in Section 5.6

#### 4.3 Co-enrolment Guidelines

It is expected that participants for the REAL trial will also be enrolled in other trials with agreement of the Chief Investigators of the trials if the Principal Investigator does not think it will be detrimental to the patients' wellbeing. Allowing enrolment into REAL at or before day 5 of cycle 1 after start of chemotherapy should help facilitate recruitment into REAL given this is a challenging time for recruiting patients into any study at the time of initial cancer diagnosis.

Patients will not be eligible if already enrolled in a randomised trial for which the primary or secondary outcomes are similar to those in the REAL trial. Patients can be enrolled in observational studies or non-randomised studies.

# 5. Treatment of Participants

#### 5.1 Introduction

This trial is a cross-over study of a control arm (threshold of ≤90 g/L) vs an intervention arm (threshold of ≤70 g/L). Participants will be randomised to be in one arm for their first cycle of treatment and the other arm for the second cycle of treatment. The arms are described in the sections below. The trial will compare two different policies for RBC transfusion, "restrictive" and "liberal". All recruited participants at a participating site should be transfused in accordance with the randomised transfusion policy for that cycle of treatment. Any transfusion required as part of the policy should be commenced within 24 hours of obtaining the haemoglobin result for inpatients and 72 hours for outpatients.

Prior to commencement of allocated transfusion policy in cycle 1, patients may receive red cell transfusions according to clinical need. This recognises the challenge of approaching and consenting patients at the time of new diagnosis and the importance of allowing patients and staff a short period of time to fully consider the trial. During this run-in period, red cell transfusion policies will be consistent with local guidelines, and typically at haemoglobin thresholds of 80g/L.

[figure not shown]
Allocation to either the restrictive or liberal policy will then apply from at or before Day 5 onwards in cycle 1. For cycle 2 chemotherapy treatment, participants will follow the alternative transfusion policy (ie if allocated to 'restrictive' arm for cycle 1, this would be the 'liberal' arm for cycle 2).

# 5.2 Intervention Arm: Restrictive Transfusion Policy (RBCs transfused when haemoglobin ≤70g/L)

Following enrolment, the haemoglobin values of participants will be recorded according to routine clinical care. If the haemoglobin value is recorded as ≤70 g/L, red blood cells should be transfused at a dose of 1 unit at a time, with the aim of keeping the haemoglobin range between 71-80 g/L. The timing of repeat haemoglobin measurements should be decided by the attending haematologist. Further red blood cell transfusions should only be administered if the haemoglobin value decreases to a value of 70g/L or less (see figure 1). Any transfusion required as part of the policy should be administered within 24 hours of obtaining the haemoglobin result (up to 72 hours for outpatients). For participants with haemoglobin values significantly lower than the threshold (i.e. where one unit would not be expected to increase the haemoglobin level into the desired range) more than 1 unit at a time may be transfused.

#### 5.2.1 Treatment Algorithm

Figure 1: Intervention Arm: Restrictive transfusion strategy

\*or 2 units for outpatients at clinician's discretion

# 5.3 Control Arm: Liberal Transfusion Policy (RBCs transfused when haemoglobin ≤90g/L)

Following enrolment, the haemoglobin values of participants will be recorded according to routine clinical care. If the haemoglobin value is recorded as ≤90 g/L, red blood cells should be transfused at a dose of 1 unit with the aim of keeping the haemoglobin range between 91-100 g/L. The timing of repeat haemoglobin measurements should be decided by the attending haematologist. Further red blood cell transfusions should only be administered if the haemoglobin value decreases to a value of 90g/L or less (see figure 2). Any transfusion required as part of the policy should be administered within 24 hours of obtaining the haemoglobin result (or 72 hours for outpatients). For participants with haemoglobin values significantly lower than the threshold (i.e. where one unit would not be expected to increase the haemoglobin level into the desired range), more than 1 unit at a time may be transfused.

[figure not shown]

Figure 2: Control Arm: Liberal transfusion strategy

\*or 2 units for outpatients at clinician's discretion

#### 5.3.1 Measurement of Haemoglobin Level

The timing and frequency of repeat haemoglobin measurement(s) is at the discretion of the attending clinician(s), guided by the patient's clinical signs and symptoms and the clinician's usual practice. It is anticipated that the haemoglobin concentration will be measured daily for most patients, but this is not mandated as part of applying the transfusion policy.

#### 5.3.2 Obtaining Blood Component

The red cell units will be obtained in the usual way from the hospital transfusion laboratory and the prescription, transfusion record and traceability will be performed as per standard hospital policy.

#### 5.3.3 Accountability

During the trial, the red blood cells issued and transfused will be recorded on the CRF and in the patient's medical record. Any untransfused units will be returned to the transfusion laboratory.

#### 5.4 Duration of randomisation

The first transfusion policy should be followed from at or before day 5 (from start of chemotherapy) of cycle 1 until the end of their first cycle of treatment. The alternate transfusion policy should be followed for the second cycle of treatment. The two cycles should be consecutive courses of intensive chemotherapy. The intention is to undertake the trial over periods of observation for predominantly inpatient stays. It is recognised that some patients may receive intensive therapy as an outpatient but the trial protocol will continue to be applied as far as possible.

#### 5.5 Clinician Discretion to Transfuse in Contravention of the Allocated Policy

Clinicians will have the discretion to transfuse, or not to transfuse, in contravention of the allocated policy but must document their reason(s). This will be done on a CRF with a choice of standardised list of reasons, including

- Acute cardiac ischaemia
- Symptomatic anaemia with significant functional impairment
- Active bleeding with anticipated further drop in haemoglobin
- On-going bleeding not responding to standard haemostatic procedures, thought to be due to low haemocrit
- Participant request/convenience (e.g. bank holiday weekend, patients with antibodies)

Non-compliance does not constitute a participant withdrawal and the patient will continue to be followed up in accordance with the allocated transfusion policies. The numbers and reasons for additional, out-of-protocol transfusions and instances when transfusions were not given when they should have been will be recorded. Possible reasons for additional transfusions outside of the protocol could include periods of bleeding, haemodynamic instability or symptomatic ischaemic heart disease. Possible reasons for not transfusing would be for fluid overload.

Patient safety is of paramount importance, and a few participants may develop significant bleeding. If the attending haematologist feels that immediate red cell transfusion is needed for the patient, regardless of, or before obtaining a further, haemoglobin result (e.g. due to clinical condition or severity of bleeding), then the participant should be managed as per local practice by clinical discretion. Such participants would remain in the trial and remain allocated to their randomised treatment schedule for further transfusion support.

If the participant declines to continue with the assigned threshold for that cycle they should also remain in the trial, unless consent for data collection is declined, see section 3.5.3.

Clinicians and participants will be encouraged to maintain the allocated threshold unless there are significant symptoms and signs considered to be due to anaemia.

#### 5.6 Unblinding

There will be an attempt to blind participants to their treatment allocation. Participants will be asked at the end of each cycle which arm they believe they have been allocated to.

Physicians will not be blinded to the allocation. All attempts should be made to conceal the allocation from the participant and participants will be counselled at enrolment that they will not be informed of their haemoglobin measurement results. Decisions to transfuse should be based on participant symptoms and clinician knowledge of haemoglobin level and treatment allocation. A decision to transfuse outside the protocol does not mandate unblinding of the participant and patients will still not routinely be informed of their haemoglobin level.

#### 5.7 Protocol Treatment Discontinuation

In consenting to the trial, participants are consenting to the trial treatment, trial follow up and data collection. However, a participant may stop treatment early or be stopped early for any of the following reasons:

- Participant moves to supportive care only prior to the end of the 2nd cycle
- Unacceptable adverse event
- Any change in the participant's condition that justifies the discontinuation of treatment in the opinion of the clinician
- Withdrawal of consent

Participants who undergo one cycle of chemotherapy and proceed straight to allogeneic stem cell transplantation will not be eligible to continue in the study following the first cycle of chemotherapy.

As the patient's participation in the trial is entirely voluntary they may choose to discontinue the trial treatment at any time without penalty or loss of benefits which they are otherwise entitled. Although the participant is not required to give a reason for discontinuing their trial treatment, a reasonable effort should be made to establish this reason while fully respecting the participant's rights.

Participants should remain in the trial for the purpose of follow up and data analysis, unless they withdraw their consent from all stages of the trial, in which case, they should be withdrawn. Data collected until the time of withdrawal will be retained and included in the analysis.

#### 5.7.1 Medications not permitted

There are no medications not permitted in this trial. For patients receiving other trial treatments see Section 4.3.

#### 5.7.2 Duration of study/end of study

The randomised transfusion policies will be followed for all eligible participants up to the end of each course of chemotherapy, for two consecutive cycles. For eligible participants, the day of randomisation is defined as (Cycle 1) Day 1 (which must be at or before Day 5 from start of chemotherapy) and the transfusion policies will be followed to the end of the second cycle of intensive chemotherapy (or death). Data collection will occur up to the end of each cycle (day +42 or the start of the next cycle) and follow up QoL assessment will take place at the end of each cycle, i.e. at admission or attendance for commencement of the next cycle of treatment. In the event that no subsequent cycle of treatment is given, participants will be contacted at day +42.

# 6. Assessments and Follow-up

#### 6.1 Trial Assessment Schedule

Information on all trial-related assessments and follow-ups is summarised in the table below

Table No 1:

Assessment to be performed	(Upto) Day 5 Cycle 1	At Consent	Cycle 1	Mid Cycle 1	Cycle 2	Mid Cycle 2	3 Months
Screen for eligibility	√						
Written consent		√					
Registration and unique ID		√					
Record baseline data		√					
Haemoglobin level(s)			V		V		
Details of RBC transfusion			V		√		
Daily assessment of bleeding			V		V		
Details of other blood			√		√		
components e.g. platelets							
Details of adjunctive			√		√		
treatments – TXA, epo							
Serious adverse events			√		√		
Response to chemotherapy			V		V		
Daily functional capacity			√		√		
score, daily visual analogue							
scale from EQ 5d (see end of							
document)							
EQ-5D-5L/ EORTC QLQ C30		V	√ (end)		√ (end)	√	
forms		Y					
Assessment of success of			√ (end)		√ (end)		
blinding							
Death							V

#### 6.2 Procedures for Assessing Efficacy

#### 6.2.1 Data Collection

Data collection will be the responsibility of the local research team led by the PI at each site. Overall responsibility for collating data from all centres will reside with the Trial Manager. Data will be recorded on paper Case Report Forms (CRFs). Three patient identifiers (Trial ID number allocated at enrolment, initials, and age) will be used on all CRFs. Centres will send copies of completed CRFs to the Trial Data Manager at the CTU, where they will be entered onto the Clinical Trial Database.

Data will be collected by the RN/PI/Designate on the relevant CRFs. All data will be anonymised with participants assigned a unique trial ID number at enrolment. The data will be checked for completeness at the site before being transmitted to the data manager for entry into the trial database. A copy of the consent form and PIS will also be filed in the patient's hospital notes.

#### 6.2.2 Source Documentation

All the source data except for randomisation and questionnaires will be found in the patient medical records at the participating site.

The quality of life questionnaires are their own source data and randomisation number will be provided by sealed envelope.

100% of the consent forms and a sample of CRFs will be checked for consistency against the source documents in the patient's hospital notes at routine monitoring visits by the Trial Manager.

#### 6.2.3 Screening Log

A screening log of all patients admitted with AML will be kept. The total number of admissions, the number of admissions meeting eligibility criteria and the number of eligible patients who provide consent to data collection and follow up will be recorded.

#### 6.2.4 Baseline Clinical Characteristics

Baseline clinical characteristics will be obtained and will include date/time of admission, age, gender, presenting symptoms, routine physiological parameters, etc. This data should be recorded at study enrolment (i.e. when consent has been confirmed).

#### 6.2.5 Laboratory and Transfusion Data

The date and time of all haemoglobin measurements will be recorded as part of standard clinical practice. A record of all haemoglobin results will be requested for each participant. All RBC transfusion episodes will be recorded, including the haemoglobin level prior to transfusion and the total number of RBC units transfused. The number and date of transfusion of other blood components specifically including platelets will be recorded.

A transfusion episode will be defined as single units or multiple units transfused with no check in haemoglobin occurring between units.

We will explore integrated IT approaches to extraction and collection of all routinely available participant data relevant to the trial on IT systems, particularly including key performance indicator data, at recruiting centres.

#### 6.2.6 Outcome Measures

Please see Section 9

#### 6.2.6.1 Monitoring/data collection outcomes

Because the study will take place at several UK sites, each with different methods of recording blood component requests, prescriptions, transfusions and outcomes as well as availability and design of electronic diagnostic decision support, the study will also seek to establish whether these impact on adherence at each centre. The study is not designed to be powered to identify significant differences.

#### 6.3 Procedures for Assessing Safety

Adverse events will be reported as described in Section 7. Bleeding episodes will be prospectively recorded with a daily bleeding score.

#### 6.4 Procedures for Assessing Quality of Life

Quality of life will be assessed using the EQ-5D-5L and EORTC QLQ C30 questionnaires. These will be completed at consent, at mid point of each cycle and again at the end of each cycle (i.e. D+42 or on commencement of the next cycle). The mid point is defined as the time of nadir cytopenia. In DA regimen, this is day 10-12 post chemotherapy; in FLAG-Ida regimen, this is day 10- 16 post chemotherapy. If the participant is unable to complete the questionnaire, it may be completed by a suitable surrogate (carer or research nurse) and reason for this documented.

#### 6.5 Other Assessments

In addition a short daily assessment of quality of life will be completed by the nurse or if at home by carer or participant.

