#### 9.2.3 Clinical Outcomes

- Death: All-cause mortality at 3 months post study completion
- **Bleeding**: Clinically significant bleeding events are defined as equivalent to WHO Grade 3 or 4. These events will be captured using definitions applied for bleeding assessments conducted using a tool based upon that used in the TOPPS trial and further developed by an international working group the BEST collaborative.
- Proportion of participants experiencing thromboembolic and ischaemic events:
   Includes myocardial infarction, stroke, pulmonary embolus, clinically overt and line-related thrombotic events. Line related blockage may have other causes related to the type of line used. (These thromboembolic and ischaemic events may be related to higher haemoglobin concentrations, although MI may occur more commonly with lower thresholds)
- Syncopal events
- Transfusion reactions
- Length of hospital stay
- Proportion of participants with at least one blood culture verified bacterial infection

- Median EQ-5D-5L Visual Analogue Scale score for symptomatic and nonsymptomatic transfusions
- Health related quality of life at baseline, middle and end of each cycle using EQ-5D-5L/ EORTC QLQ C30 forms)

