# **Appendix**

#### Appendix 1. ECOG/WHO/Zubrod score

The Eastern Cooperative Oncology Group (ECOG) score (published by Oken *et al.* in 1982), also called the WHO or Zubrod score (after C. Gordon Zubrod), runs from 0 to 5, with 0 denoting perfect health and 5 death: [2]

- 0 Asymptomatic (Fully active, able to carry on all predisease activities without restriction)
  - 1 Symptomatic but completely ambulatory (Restricted in physically strenuous activity but ambulatory and able to carry out work of a light or sedentary nature. For example, light housework, office work)
  - 2 Symptomatic, <50% in bed during the day (Ambulatory and capable of all self care but unable to carry out any work activities. Up and about more than 50% of waking hours)
  - 3 Symptomatic, >50% in bed, but not bedbound (Capable of only limited self-care, confined to bed or chair 50% or more of waking hours)
  - 4 Bedbound (Completely disabled. Cannot carry on any self-care. Totally confined to bed or chair)
  - 5 Death

Adapted for patient to fill in on a daily basis:

- 0 Asymptomatic (Fully active, able to carry on all activities without restriction)
- 1 Symptomatic but completely ambulatory (Restricted in physically strenuous activity but ambulatory and able to carry out work of a light or sedentary nature. For example, light housework, office work)
- 2 Symptomatic, <50% in bed during the day (Ambulatory and capable of all self care but unable to carry out any work activities. Up and about more than 50% of waking hours)
- 3 Symptomatic, >50% in bed, but not bedbound (Capable of only limited self-care, confined to bed or chair 50% or more of waking hours)
- 4 Bedbound (Completely disabled. Cannot carry on any self-care. Totally confined to bed or chair)

Guidelines for patient reported outcomes in Haematology. EHA Scientific working group; Eds A. Novik, S. Salek, T. Ionova

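### Section 6.5 has the nurse complete inpatients' daily quality-of-life score unconditionally, against Appendix 1 and section 6.4; if the nurse rates rather than transcribes, participant blinding no longer protects the score

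*Protocol*

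**What the plan says.** Four parts of the protocol bear on who supplies the daily score.

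- **Section 6.5:** "In addition a short daily assessment of quality of life will be completed by the nurse or if at home by carer or participant". No inability condition is attached, and nothing requires the completer to be recorded.
- **Section 6.1, Table 1:** in both cycles it lists a daily functional capacity score and a daily VAS taken from the EQ-5D, and points to the end of the document. Appendix 1 there sets out an ECOG-type scale under the line "Adapted for patient to fill in on a daily basis".
- **Section 6.4:** for the full EQ-5D-5L and EORTC QLQ-C30 questionnaires, if the participant is unable, "it may be completed by a suitable surrogate (carer or research nurse"), and the reason must be documented.
- **Section 5.6:** "There will be an attempt to blind participants to their treatment allocation", and "Physicians will not be blinded to the allocation". Nurses are not mentioned, and no section provides for a blinded assessor.

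Two further statements set the reach of the issue. Section 5.4 says: "The intention is to undertake the trial over periods of observation for predominantly inpatient stays". Section 9.2.3 lists as a clinical outcome: "Median EQ-5D-5L Visual Analogue Scale score for symptomatic and nonsymptomatic transfusions".

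**The concern.** Functional capacity and the VAS are subjective. The protocol takes trouble to keep participants unaware of their allocation: haemoglobin results are not routinely given to them, and they are asked which arm they think they are in. That effort protects a subjective score only while the participant is its source. If a ward nurse forms the rating, and knows the haemoglobin or the transfusion policy in force, expectation can enter the score.

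The cross-over does not fully remove this. A nurse's constant tendency to score high or low may cancel within a participant, but a tendency that depends on the strategy in force does not.

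The VAS outcome in section 9.2.3 could be touched in another way. Section 5.5 lists symptomatic anaemia as a reason to transfuse outside the policy. If the same ward staff judge symptoms and score the VAS, the score and the symptomatic label are not independent.

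What is at stake is the usefulness of a secondary measure. Section 1.3 argues that quality of life and symptomatic anaemia matter more in this population than in intensive care, and the study is meant to inform a larger trial, into which the procedure could carry over.

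**Working it through.** The plan states no figure on this point, so the check is a comparison of the texts.

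1. **Which instruments are meant.** Section 6.5 does not name them. Table 1 has only two daily quality-of-life items, the functional capacity score and the VAS, so I take section 6.5 to refer to these.

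2. **Who completes them.**

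| Measure | In hospital | At home | Condition for a proxy |
|---|---|---|---|
| Daily score, section 6.5 | Nurse | Carer or participant | None stated |
| Daily functional scale, Appendix 1 | Patient | Patient | None stated |
| Full questionnaires, section 6.4 | Participant | Participant | Participant unable; reason documented |

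   For the functional scale in hospital, the first two rows disagree. The adapted scale in Appendix 1 also drops the category for death that the standard scale has, which fits a form the patient fills in. For the VAS, Appendix 1 is silent. The mismatch there is with the principle of section 6.4 and with section 9.2, which describes questionnaire quality of life as self-reported by the patient.

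3. **How often it applies.** Section 5.4 expects observation to be mainly inpatient, so on the wording of section 6.5 the nurse would be the completer on most days.

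4. **Whether the completer may be unblinded.** Section 5.6 limits blinding to participants and states that physicians are unblinded. Nothing extends blinding to nurses. It follows that a nurse may know the allocation or the haemoglobin, not that every nurse does.

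5. **Where the scores are used.** The daily functional score is not named in section 9.2. The one outcome that names the VAS is split by symptomatic versus non-symptomatic transfusion. Section 9.4 says in general terms that the two strategies will be compared, without naming the daily scores. Questionnaire scores, which are compared by arm, fall under the stricter rule of section 6.4.

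6. **Whether a size can be given.** The protocol gives no standard deviation, within-person correlation or proxy-to-self agreement for either daily score. No bias can be computed.

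**The case against.** The strongest reply is that completion by the nurse may mean only that the nurse writes down what the patient says. Section 6.5 would then be compatible with Appendix 1, and the defect would be loose wording rather than a biased procedure. That reading is possible and cannot be excluded. But section 6.5 does not say so, and the contrast it draws between the nurse in hospital and the carer or participant at home leaves room for the other reading. The wording needs settling either way.

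Other limits also stand. Appendix 1 covers the functional scale and not the VAS. The change of rater between ward and home would bias a comparison of strategies only if the share of inpatient days differed between them, and nothing in the protocol shows that it would.

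A reader might infer more than the text supports in three ways.

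- **That unblinded staff score the patients.** The protocol never says that nurses know the allocation; this is a possibility inferred from participant-only blinding.
- **That a named comparison between strategies is biased.** No listed outcome compares the daily scores by strategy.
- **That the bias can be sized from section 9.3.** Its SD of 20 and correlation of 0.25 describe haemoglobin in g/L. Applied to the VAS with 36 pairs they give SE = 20 × √(2 × 0.75/36) = 4.08 points, and a shift of about 8.3 points would be needed for significance on a paired t-test with 35 degrees of freedom. These figures say nothing about the VAS and are not evidence of size.

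**Conclusion.** The point holds as a minor one. Sections 6.5 and 6.4 and Appendix 1 do not give one rule for who supplies the daily score, and section 6.5 allows a possibly unblinded nurse to rate a subjective measure on most trial days, with no need to show that the participant could not answer.

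The conclusion on bias rests on two assumptions: that nurses would rate rather than transcribe, and that some would know the allocation or haemoglobin. If either fails, what remains is an inconsistency of wording. The size of any bias is unknown. Both primary outcomes are based on pre-transfusion haemoglobin and are untouched, and the full questionnaires already have an adequate surrogate rule.

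**What to change.** Reword section 6.5 to agree with Appendix 1 and section 6.4:

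- the participant gives the daily functional score and VAS in hospital and at home, and a nurse may write the answer down;
- a nurse or carer answers as proxy only when the participant is unable;
- the completer and the reason for any proxy are recorded each day, so that proxy scores can be identified in the analysis.

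The cost is a change of protocol wording and one CRF field, if the CRF (not at hand) does not already have it. There may be fewer self-reports on the days when participants are sickest; proxy scores would still be collected then and would be marked as such. How they enter the analysis can be left to the statistical analysis plan.
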